## 3.3 Source of Study Participants

- a. Participants will be recruited at 8 NCORPs within the URCC Research Base network
- b. Eligible participants will be aged 18 or older because the TENS device is not approved for children

Racial Categories	Not Hispanic or Latina:	Not Hispanic or Latino:	Hispanic or Latina:	Hispanic or Latino:	Total
	Female	Male	Female	Male	
American Indian/Alaska Native	0	0	0	0	0
Asian	6	2	0	0	8
Native Hawaiian or Other Pacific Islander	1	0	0	0	1
Black or African American	10	6	2	0	18
White	83	34	2	1	120
More Than One Race	1	1	1	0	3
Total	101	43	5	1	150

 Table 3. Planned Enrollment Table

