#### 4.4 Coordinator requirements

Up to 10 NCORPs will be allowed to participate in the study; participating NCORPs will be determined by the PI, [name], based on their interest and demonstrated ability to open the study at their sites. If at all possible, each site should have 2 coordinators available to participate in the study. One will be blinded to the treatment assignment (i.e., "assessor") and will perform all of the assessments and the other will know the treatment assignment (i.e., "unblinded coordinator") and will introduce the study to the participant, teach them how to use the TENS device, and answer any phone calls regarding trouble shooting of the device. If it is not possible for the site to have 2 coordinators dedicated to the study, a single coordinator can perform all of the study activities as long as they complete both trainings. The fact that there is one coordinator should be documented so that the potential effect of the lack of blinding on the outcomes can be assessed. If only one coordinator is available at a site, all places in the remainder of the protocol that refer to the "blinded" or "unblinded" coordinator should be interpreted as the "coordinator" for that site. Sites who only have one coordinator available must obtain permission from the study PI to use a single coordinator for both roles. Permission can be requested by emailing the study mailbox at URCC\[contact].

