### 5.3.4 Randomization/Stratification

A computer-generated randomization schedule will be used to randomize participants 1:1 to the two intervention conditions stratified by study site in random block sizes of 2 and 4. The schedule will be prepared by a URCC NCORP Research Base biostatistician. The coordinator will use the Randomization form in REDCap to obtain the randomization assignment at the Baseline Visit.

The two study arms are as follows:

- a. Active TENS Device
- b. Placebo TENS Device

A total enrollment of 150 participants is planned, with up to 75 participants randomized to each intervention group. Note, that participants who discontinue prior to randomization (i.e., between the screening and baseline visits) will not be replaced. It should take approximately 12 months to accrue all participants.

Week	Screening And Registration	Randomization	Distribution of Study Device	Self- Report Measures	Functional Exam Measures	Coordinator open participant Quell App	Adverse Event Monitoring
Screening (Visit 1)	х						
Baseline (Visit 2)		х	х	Х	Х		
1							Х
2							
3							Х
4							
5							Х
6 (Visit 3)				Х	Х	Х	Х

Table 5. Schedule of Events\*

\*Daily diary completed between screening and baseline visit and during Weeks 4 (i.e., day 21 - 28) and 6 (i.e., day 35 - 42). Participants will be called 4 weeks after the end of the study (i.e., Week 10) and asked if they are using the commercial device).

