## 10. STATISTICAL CONSIDERATIONS

**10.1 Quality Control.** Established standardized data quality procedures are used for all URCC NCORP Research Base studies. Data will be entered on scannable (Teleforms) or electronic forms in REDCap and electronically transferred to Microsoft Office databases. Data will be inspected visually. Data distributions will be evaluated to identify any outliers that will be inspected for possible mistakes. If no mistake is found for an outlier, it will remain in the data. Statistical analyses will be performed using SAS, JMP, or R as appropriate.

**10.2 Analysis set and Missing Data.** All participants who are randomized will be included in the analyses. All efforts will be made to prevent missing data. We will use multiple imputation methods that assume missing at random for the primary and secondary analyses. A sensitivity analysis using pattern mixture methodology that assumes missing not at random will be used to evaluate the impact of missingness on the results.

**10.3 Sample Size Estimation.** Since this is a phase II preliminary efficacy trial, the primary analysis will be performed at the two-tailed 20% significance level (i.e., alpha=0.2). A sample size of 126 evaluable participants will provide 80% power to detect a 0.4 effect size (standardized mean difference) in the primary analysis. Assuming 15% withdrawal, we will randomize 150 participants.

**10.4 Primary Analysis.** The effects of TENS on CIPN will be estimated using analysis of covariance (ANCOVA). The model will include CIPN20 at Week 6 as the outcome, treatment group as the factor, and study site and the baseline CIPN20 score as covariates. Additionally, to explore potential large impacts of cancer type, chemotherapy class (i.e., platinum, taxane, other), and analgesic consumption ( $\geq$ 30% vs. <30% decrease in number of days acetaminophen and/or NSAIDs were taken), we will add these factors to the above model for sensitivity analyses. We will also perform subgroup analyses separately based on these factors to identify possible differential intervention effects to inform the design of a future study. Distributional assumptions (e.g. normality of residuals) will be evaluated and, if necessary, appropriate transformations or nonparametric methods will be used.

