## 10.6 Exploratory Analyses.

(1) ANCOVA analysis as in the primary will be used to investigate the effects of TENS on exploratory outcomes (i.e., balance (SPPB balance subscale), descending inhibition (CPM test), physical function (PROMIS short form), CIPN-interference in daily life, CIPN measured by TNAS and CIPN symptom inventory composite measure, depression and anxiety (PROMIS short forms)) at baseline and at Week 6 visits.

(2) Analysis of variance (ANOVA) or an appropriate non-parametric method (e.g., Wilcoxon test) if the normality assumption is not satisfied will be used to evaluate the between arm differences in participant-perceived changes in CIPN symptoms and participant-perceived change in ability to be active.

(3) Descriptive statistics will be used to characterize the distribution of descending inhibition as measured by CPM at baseline. Additionally, the correlation of descending inhibition with CIPN severity (via CIPN20, TNAS, and symptom NRS scores) will be evaluated using a Spearman's correlations.

(4) To explore the predictive effects of baseline descending inhibition on response to TENS, ANCOVA analysis will be used to investigate whether baseline descending inhibition predicts the effect of TENS on CIPN. The model will include CIPN20 at Week 6 as the outcome, baseline CPM test result, treatment group, and baseline CPM test result x treatment group interaction as factors, and study site and the baseline CIPN20 score as covariates.

(5) To explore mechanistic associations between changes in descending inhibition and CIPN symptoms, we will use mediation analysis technique (the method initially formalized by Baron and Kenny, extended to clinical trial settings by Kraemer, and methodologically updated by MacKinnon et al.). Specifically, we will use path modeling to estimate indirect (mediation) effects of changes in the CPM test on CIPN symptoms, and bootstrapping to estimate the 95% confidence intervals. The MPlus software will be utilized.

(6) The proportion of participants who decreased "as-needed" usage of acetaminophen and NSAIDs (defined as taking acetaminophen or NSAIDs, on average, at least 30% fewer days per week in the last week of the trial compared to the baseline week) will be compared by groups using a Chi-Square test.

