(7) The proportion of participants who report, for the impression of change in CIPN symptoms question "very much improved", "much improved", "minimally improved", "no change", "minimally worse", "much worse", and "very much worse") will be compared between treatment groups using a Cochran Armitage Trend Test.

(8) The proportion of participants whose sensation threshold from the monofilament test improved will be reported together with the 95% confidence interval (CI) and tested against the null hypothesis of no improvement.

(9) Descriptive statistics and 95% CIs will be used to assess the percentage of participants and outcome assessors that correctly identify the group to which the participant was assigned as well as the basis for the guesses.

(10)Test, re-test reliability for the CPM test will be evaluated using Intraclass correlation coefficients (ICCs). Test, re-test reliability for the lower limb sensation threshold test will be measured using Kappa statistics.

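### Exploratory tests (2), (6) and (7) name no adjustment for the site stratification, and the CIPN impression item is tested twice: a small power cost, and only if site predicts the outcome

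*Combined protocol and SAP*

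**What the plan says.** Section 5.3.4 sets 1:1 randomisation, "stratified by study site in random block sizes of 2 and 4". On the number of sites, Section 3.3 says "Participants will be recruited at 8 NCORPs within the URCC Research Base network" and Section 4.4 says "Up to 10 NCORPs will be allowed to participate in the study".

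Site enters the primary ANCOVA (Section 10.4). It enters the secondary analyses (Section 10.5) and exploratory analysis (1) because these are specified to follow the primary model. Exploratory analysis (4) names it explicitly.

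Three between-arm comparisons in Section 10.6 do not mention it:

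- (2) compares participant-perceived change in CIPN symptoms and in ability to be active by ANOVA, or by a non-parametric test such as the Wilcoxon if normality fails. No model terms are listed.
- (6) takes the proportion of participants who cut their days of acetaminophen or NSAID use by at least 30%; this "will be compared by groups using a Chi-Square test".
- (7) takes the seven response categories of the CIPN impression question; these "will be compared between treatment groups using a Cochran Armitage Trend Test".

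The CIPN impression is a single item on a 1 to 7 scale (Section 5.4), so (2) and (7) test the same variable. Section 10 states an alpha for the primary analysis only (0.20, two-sided). It gives no alpha or power target for the exploratory tests.

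**The concern.** Blocking within site keeps the arms nearly balanced at each site, so differences between sites largely cancel out of the treatment comparison. A test that ignores site still counts those differences in its standard error. If site predicts the outcome, that standard error is too large, the test rejects less often than its nominal level, and some power is lost. The rest of Section 10 avoids this by adjusting for site, and no reason is given for treating these three comparisons differently.

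The duplication is a separate matter and needs no assumption about sites. The CIPN impression item can produce a p-value from (7) and another from (2), where the method may switch after a normality check. Nothing says which one is the result for that item. The trial is meant to inform a phase III design, so a single clear analysis per item is worth having.

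**Working it through.** **1. Inputs.** From the documents: 1:1 allocation, site strata, blocks of 2 and 4; 8 planned sites, at most 10; 150 randomised and 126 evaluable. Assumed, because the documents give no figure: the between-site ICC, a nominal two-sided 5% level, a 38% event rate, a treatment effect of 0.5 SD on the underlying scale, and the pattern of site sizes.

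**2. The plan's own figure.** No size or power is stated for (2), (6) or (7). The nearest figure, for the primary analysis, is "A sample size of 126 evaluable participants will provide 80% power to detect a 0.4 effect size (standardized mean difference) in the primary analysis". The normal approximation gives n per arm = 2(1.282 + 0.842)²/0.4² = 56.4, so 57 per arm and 114 in total. With 63 per arm, power is 83%. The stated 126 therefore errs on the safe side, and would match an effect of 0.378, which rounds to 0.4. Allowing 15% withdrawal, 126/0.85 = 148.2, so 149, close to the stated 150. None of this bears on the present point; 126 is used below only as the evaluable number.

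**3. Direction, by formula.** Let R² be the share of outcome variance explained by site. With exact within-site balance and no losses, the unstratified statistic has variance 1 − R² instead of 1. For a nominal 5% test with 80% power (noncentrality 1.960 + 0.842 = 2.802):

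- size = 2[1 − Φ(1.96/√(1 − R²))]
- power = Φ(2.802 − 1.96/√(1 − R²))

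| R² | 1.96/√(1 − R²) | Size | Power |
|---|---|---|---|
| 2% | 1.980 | 4.8% | 79.4% |
| 5% | 2.011 | 4.4% | 78.5% |
| 10% | 2.066 | 3.9% | 76.9% |

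The direction is conservative. These figures are best read as an upper bound, because incomplete blocks and withdrawals loosen the balance and the stratified comparator is treated as costless.

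**4. Size, by simulation.** 6,000 trials per setting: 150 randomised by site in random blocks of 2 and 4, and 16% lost at random (1 − 126/150 = 0.16), with 8 equal or 10 unequal sites. ICC is on the underlying scale. Chi-square is compared with CMH by site; the seven-category trend test is compared with a site-stratified mean-score test. Rejection rates at nominal 5%:

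| ICC | Sites | Size: chi-square / CMH | Power: chi-square / CMH | Size: trend / stratified | Power: trend / stratified |
|---|---|---|---|---|---|
| 0 | 8 | 0.054 / 0.054 | 0.596 / 0.591 | 0.051 / 0.050 | 0.774 / 0.767 |
| 0 | 10 | 0.048 / 0.045 | 0.596 / 0.586 | 0.054 / 0.053 | 0.761 / 0.756 |
| 0.01 | 8 | 0.054 / 0.054 | 0.600 / 0.594 | 0.050 / 0.050 | 0.767 / 0.761 |
| 0.01 | 10 | 0.050 / 0.050 | 0.606 / 0.597 | 0.050 / 0.050 | 0.767 / 0.758 |
| 0.05 | 8 | 0.054 / 0.053 | 0.600 / 0.604 | 0.051 / 0.055 | 0.765 / 0.770 |
| 0.05 | 10 | 0.045 / 0.044 | 0.598 / 0.600 | 0.044 / 0.048 | 0.757 / 0.760 |
| 0.10 | 8 | 0.044 / 0.046 | 0.570 / 0.581 | 0.044 / 0.051 | 0.749 / 0.766 |
| 0.10 | 10 | 0.046 / 0.050 | 0.569 / 0.577 | 0.044 / 0.049 | 0.744 / 0.758 |
| 0.20 | 8 | 0.044 / 0.056 | 0.535 / 0.571 | 0.034 / 0.047 | 0.706 / 0.764 |
| 0.20 | 10 | 0.040 / 0.046 | 0.519 / 0.555 | 0.042 / 0.052 | 0.692 / 0.746 |

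The Monte Carlo standard error of a size figure is √(0.05 × 0.95/6000) = 0.003.

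- ICC up to 0.05: power differs by at most 1 point either way; stratifying costs 0.5 to 1.0 points at ICC 0 and 0.01.
- ICC 0.10: the unstratified tests lose 0.8 to 1.1 points (chi-square) and 1.4 to 1.7 points (trend).
- ICC 0.20: they lose 3.6 points (chi-square) and 5.4 to 5.8 points (trend).

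At a nominal 20% level, the losses at ICC 0.20 shrink to about 2 points (1.6 to 2.4).

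**5. The duplicate test.** With equally spaced scores, and r the correlation between arm and score, the trend statistic is N·r² and the ANOVA F is (N − 2)r²/(1 − r²). With N = 126 and a trend statistic of 1.246, r² = 1.246/126 = 0.00989 and F = 124 × 0.00989/0.99011 = 1.24. So if (2) uses ANOVA, (7) adds almost nothing; if (2) uses the Wilcoxon, two competing p-values remain.

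**The case against.** These are exploratory tests. Neither global impression nor analgesic reduction appears in any listed aim, and a slightly conservative p-value cannot create a false claim of efficacy. Unadjusted tests are valid and simple to report. At an average of 126/10 = 12.6 to 126/8 = 15.75 evaluable participants per site, some strata may be very small or have one arm only, and these contribute little or nothing to a stratified test. All of this stands, and it keeps the point minor.

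A reader might go further and infer three things that the documents do not support:

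- **That the p-values are certainly conservative and power certainly lost.** This depends on how strongly site predicts these outcomes, and no between-site variance is given. Site differences are plausible, since Section 4.4 allows some sites a single coordinator in both the blinded and unblinded roles, but plausibility gives no size.
- **That stratifying is free.** It costs up to about 1 point of power when site has no effect.
- **That (2) excludes site.** It lists no model terms, so site is unspecified rather than ruled out.

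The duplicate testing of the CIPN impression item does not support the site argument, but it follows from the text alone and no objection removes it.

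**Conclusion.** The point holds as a minor inconsistency within Section 10. Exploratory (6) and (7) name unstratified tests and (2) names no site term, although the trial randomises by site and its ANCOVA models adjust for it. The CIPN impression item has two overlapping analyses.

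The consequence is conditional: the tests are conservative to the extent that site predicts the outcome. At an assumed 5% level the loss is undetectable at ICC up to 0.05, about 1 to 2 points of power at 0.10, and about 4 to 6 points at 0.20. These figures rest on the assumed ICC, event rate, effect and site sizes. They come from the chi-square and trend tests; the ANOVA in (2) should behave like the trend test, since the two statistics nearly coincide. The Wilcoxon, van Elteren and proportional odds analyses were not simulated.

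A reader might also infer that the error rate is inflated or that the primary result is affected. Neither follows: the direction is conservative, and the primary model already includes site.

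**What to change.** In Section 10.6:

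- For (6), replace the chi-square test with a CMH test stratified by site.
- For each global impression item (CIPN symptoms and activity), pre-specify one site-stratified ordinal test, either van Elteren or proportional odds with site, in place of the overlapping tests in (2) and (7).
- State in advance how very small sites will be pooled.
- State the nominal level, if any, at which these tests will be read.

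If the sponsor prefers unadjusted tests, saying so and naming one test for the CIPN impression item would be an adequate answer.

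The cost is SAP wording, slightly more analysis work, and up to about 1 point of power if site turns out to have no effect. No data collection or sample size change is needed.

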## 2. AIMS/OBJECTIVES

- **2.1 Primary Aim.** Obtain efficacy estimates of daily TENS on CIPN (European Organisation for Research and Treatment of Cancer-CIPN20 (EORTC-CIPN20)) to inform the design of a phase III confirmatory trial.
- **2.2 Secondary Aim 1.** Obtain efficacy estimates of TENS on individual CIPN symptoms (i.e., hot/burning pain, sharp/shooting pain, tingling, numbness, cramping (measured daily via 0 10 Numeric Rating Scale (NRS)).
- **2.3 Secondary Aim 2.** Evaluate the feasibility of conducting, within the URCC NCORP network, a multisite, modified double-blind RCT of TENS for CIPN with physiologic assessments of descending inhibition (i.e., conditioned pain modulation (CPM) test) by assessing the proportions of (a) screened patients who enroll, (b) randomized participants who adhere to the treatment and complete the primary assessment, and (c) randomized participants who complete the CPM test.
- **2.4 Exploratory Aim 1** Investigate the potential effects of TENS on balance, physical function, descending inhibition, lower limb sensation, and anxiety and depression.
- **2.5 Exploratory Aim 2** Establish data to support the construct validity of the Treatment-Induced Neuropathy Assessment Scale (TNAS) and CIPN symptom inventory daily diary by comparison to the EORTC-CIPN20, which is the most commonly used measure of CIPN.

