## 5.3 Schedule of study procedures

# 5.3.1 Screening / Consent Visit (Day -7; -2/+3 days) (approximately 1 hour)

Eligible participants who provide informed consent will be registered and given the daily diary of CIPN symptoms and rescue pain medication consumption, and trained on how to complete it at home during the Baseline Week (i.e., between the Screening and Baseline Visits). They will complete the CPM test and lower limb sensation test. Chemotherapy treatment notes will be collected for all consented participants.

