## 5.3.3 Baseline Visit (Day 0) (approximately 1 hour)

All participants will be randomized according to procedures in **Section 5.3.4** after they arrive for the baseline visit. They will complete the PROs, balance tests, CPM test, and lower limb sensation test. At this time the participants will be given the TENS device (see **Section 5.2** for details of the device) and sufficient electrodes for 6 weeks of the study. They will be trained on how to use the TENS device. Using a standardized script to limit variation in expectations, the unblinded coordinator will lead all participants through the calibration process to identify their ideal intensity setting. The unblinded coordinator will train the participants on how to use the device at home. The unblinded coordinator will also download the Quell Health Account App to the participant's smartphone or other device (e.g., iPad) and create a Quell Health Account using a de-identified Study Email for the participant. The Study Email will be NCORP19085xxx[xxx=participant ID number]@mail.com.

The coordinator will then train the participant to use the App to start the TENS therapy and to open the App at least 1x per day when their mobile device or tablet is connected to the internet so that their deidentified usage data will be uploaded to the cloud. Participants will be asked not to modify settings in the App other than the intensity on the main screen for the 6 weeks of the study. The usage data (i.e., number of sessions per day, time the device is on the skin, and the intensity of the last session that occurred before connecting the device to the internet) will be downloaded from the Quell Health Account by the TENS device manufacturer and provided to the research team for use in promoting adherence (see **Section 5.3.7 Phone calls**). The participants will be given a daily diary to complete during Weeks 4 (i.e., day 21 - 28) and 6 (i.e., day 35 - 42) in which they will record their daily symptoms and rescue pain medication consumption.

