# 5.3.8 End of Study Visit (Day 42; +/- 5 days) (approximately 1 hour and 15 minutes)

All participants will complete the patient-reported outcome measures, balance tests, conditioned pain modulation test, and lower limb sensation test. The coordinator will also review the list of medications that the participant reported using for CIPN at the beginning of the study and ask the participant if they changed dosages of any of the medications. Any changes will be recorded in the Changes in concomitant analgesic medications form. The coordinator will ask the participant for their device and open the Quell App to ensure final data transfer to the cloud. The data will then be downloaded by the device manufacturer and sent to the Research Base. If the participant does not come to the Week 6 visit, the coordinator will call them up to 3 times to try to reschedule the visit. The rescheduled visit can occur up to 1 month after the date of the 6-week visit. If the participant agrees to come back in, they will be encouraged to keep using the device until the rescheduled visit date.

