**Lower-limb sensation threshold.** Lower limb sensation will be evaluated using a monofilament test threshold test. In the monofilament test, the participants are asked to close their eyes while each monofilament is applied (or not) to the dorsum of the big toe in random order 10 times (i.e., trials). With each trial, the participant is asked to state whether they think the filament touch their skin. For each set of 10 trials with a single monofilament, if the participant guesses correctly  $\geq$  9 times the next weaker monofilament is used. If the participant guesses correctly 7 or 8 times this filament is documented as the participant's sensation threshold. If the participant guesses correctly  $\leq$  6 times the next stronger filament is trialed. The participant's sensation threshold is the outcome of the test. Results will be recorded on the Scoring Sheet for the Lower Limb Sensation test and then entered in REDCap in the Lower-limb sensation threshold data collection form.

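### Section 10.6(8) is the only effect analysis of the monofilament threshold and does not compare the arms, so it cannot answer the lower limb sensation part of Exploratory Aim 1

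*Combined protocol and SAP*

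**What the plan says.** Section 2.4 (Exploratory Aim 1) sets out to "Investigate the potential effects of TENS on balance, physical function, descending inhibition, lower limb sensation, and anxiety and depression".

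Section 10.6(1) applies the primary ANCOVA, which has treatment group as its factor, to a list introduced by i.e. The list begins "balance (SPPB balance subscale), descending inhibition (CPM test), physical function (PROMIS short form), CIPN-interference in daily life" and goes on to the TNAS, the symptom inventory composite, depression and anxiety. Lower limb sensation is not on it.

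The outcome appears instead in Section 10.6(8), where the proportion whose threshold on the "monofilament test improved will be reported together with the 95% confidence interval (CI) and tested against the null hypothesis of no improvement". The item does not say whether the proportion is pooled or given by arm. It does not define improved, and it does not define the null.

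The neighbouring items do name a comparison. Item (2) is about differences between arms, item (6) ends "will be compared by groups using a Chi-Square test", and item (7) compares treatment groups with a trend test. The only other analysis of the sensation test, in 10.6(10), is test-retest reliability.

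The test is done at three visits: at Screening (5.3.1, "They will complete the CPM test and lower limb sensation test"), at the Baseline Visit (5.3.3, "They will complete the PROs, balance tests, CPM test, and lower limb sensation test"), and at Week 6 (5.3.8, "balance tests, conditioned pain modulation test, and lower limb sensation test").

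**The concern.** In a 1:1 placebo-controlled trial, the effect of TENS is the difference between the arms. Placebo response, practice on the test, regression to the mean and measurement noise can all move a threshold in the favourable direction. Only the placebo arm can take these out.

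A pooled one-sample test mixes active and placebo participants. Separate tests in each arm do not help either: one arm significant and the other not is not a test of their difference. A statistician who follows 10.6(8) as written would produce a p-value that does not bear on the aim.

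The other Aim 1 outcomes all get a between-arm analysis through 10.6(1). This one does not, although the data for it are collected in both arms.

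**Working it through.** Section 10.6(8) states no figure, so there is none to reproduce. The check is how the one-sample test behaves when TENS has no effect.

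**Inputs.** Section 10.3 gives 126 evaluable participants with 1:1 allocation, hence 126 / 2 = 63 per arm. That number was set for the CIPN20 analysis and is borrowed here. The documents give no rate of improvement or worsening on the monofilament test, so every rate below is an assumption.

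**Reading A: the null is a proportion of zero.** One improved participant refutes it. With true improvement rate p, the chance of rejection is 1 − (1 − p)^n. At p = 10% in both arms:
- n = 63: 1 − 0.9^63 = 99.9%.
- n = 126: 1 − 0.9^126 = more than 99.99%.

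**Reading B: the null is improved = worsened.** This is an exact sign test at two-sided 0.05. Both arms were simulated with the same rates, so the TENS effect is zero (20,000 trials per row).

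| Improved / worsened, both arms | Net shift | Pooled test significant in favour (n = 126) | Active significant, placebo not |
|---|---|---|---|
| 28% / 28% | 0 | 1.9% | – |
| 33% / 23% | 10 points | 28.3% | 11.9% |
| 35% / 20% | 15 points | 58.8% | 21.2% |
| 38% / 18% | 20 points | 83.6% | 24.2% |

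The exact figure depends on the split as well as the shift. Separate runs with 30% / 20% and 35% / 15% gave 31% and 88% for the pooled two-sided test.

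Under the same conditions, the 95% Newcombe interval for the between-arm difference in proportion improved excluded zero in 5% to 6% of trials, as it should.

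**Precision of the replacement.** With 30% improved in both arms and 63 per arm, the 95% half-width for the difference is 1.96 × √(2 × 0.30 × 0.70 / 63) = 16.0 points. As an example with invented counts, take 27/63 (42.9%; Wilson 31.4% to 55.1%) against 18/63 (28.6%; Wilson 18.9% to 40.7%). The difference is +14.3 points. The Newcombe limits are:
- lower: 14.3 − √((42.9 − 31.4)² + (40.7 − 28.6)²) = −2.4;
- upper: 14.3 + √((55.1 − 42.9)² + (28.6 − 18.9)²) = 29.9.

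**Illustration of test noise only.** Section 5.4 says: "If the participant guesses correctly 7 or 8 times this filament is documented as the participant's sensation threshold". If a participant who feels nothing were right on each trial independently with probability 0.5, seven or more correct would occur in (120 + 45 + 10 + 1) / 1024 = 17.2% of sets. The 0.5 is an assumption: the section gives no ratio of real to blank applications. With five of each, someone who always answers no scores exactly 5. Retest simulations built on the same 0.5 floor, with assumed filament sets and slopes, gave 22% to 36% improved with no true change. The conclusion does not rest on these figures.

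**The case against.** The strongest reply is that this is one of ten exploratory items, that no decision rule or error rate hangs on it, and that the analysts can compare the arms when the data arrive. That stands, and it limits the severity. It does not remove the gap: the text names a one-sample null where its neighbours name a group comparison, so an arm comparison would be unplanned.

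Three stronger readings are tempting, and the documents do not support them.

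- A reader might infer that a significant result is to be expected even if TENS does nothing. That needs a null of exactly zero, which the text does not require, or a shared net improvement, which the documents do not give. With symmetric noise and improved set against worsened, the favourable rate is about 2%; at a 10-point shared shift it is 28%. The supported statement is that it can happen.
- A reader might infer that the item ignores participants who got worse. One possible meaning of the null sets improved against worsened and does count them. The wording is ambiguous, and no more than that can be said.
- A reader might infer that a false sensory benefit would steer the phase III trial. The primary aim ties phase III design to CIPN20 estimates, and Section 5.4 looks for the future primary outcome among three patient-reported measures. Nothing makes monofilament change a criterion.

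**Conclusion.** The point holds and is minor. Section 10.6(8) plans no between-arm comparison, no other section supplies one, and so the lower limb sensation part of Exploratory Aim 1 has no analysis that answers it. This follows from the text alone and needs no assumed rate.

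The chance of significance with no TENS effect does rest on assumptions: the reading of the null, the rates chosen for both arms, and 126 participants with usable monofilament data. Across those readings it runs from about 2% to near certainty. The range shows that the result could not be interpreted as a TENS effect; it is not a forecast of what this trial would find.

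**What to change.** Replace the one-sample test in 10.6(8) with a single between-arm comparison from the Baseline Visit to Week 6, labelled exploratory. Either form will do:

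- Tabulate improved, unchanged and worsened by arm, and give the active-minus-placebo difference in proportion improved with a 95% CI (Newcombe, for example). State how many filament steps count as improved.
- Fit an ordinal model of the Week 6 threshold with treatment, baseline threshold and site, in line with 10.6(1). This keeps the grading of the threshold.

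The cost is a sentence in the plan and one table or model, with no new data. The drawback is a wide interval, about 16 points either side for the proportion improved at 63 per arm, so only a large difference would stand out. A Screening-to-Baseline table and counts at the weakest and strongest filaments could be added, but the defect does not require them. The first spans about 7 days against 42 and is not a matched noise reference.
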